4.2 METHOD OF TREATMENT ASSIGNMENT AND BLINDING

Randomization will be performed centrally using an interactive voice or Web-based response system (IxRS). After screening, participants who meet all eligibility criteria will be randomly assigned to one of two treatment groups (gantenerumab or placebo). The ratio will be 1:1, one active to one placebo. The randomization method will be stratified block-randomization. Randomization to treatment allocation will be stratified by

geographic region (Western Europe and Australia vs. Rest of the World vs. North America), participant *APOE* ε4 status (carrier vs. non-carrier), participant stage of disease (prodromal vs. mild AD), use of AD medication (present vs. absent), and participation in the longitudinal amyloid and tau PET substudies. Except in circumstances in which a health authority, EC, or IRB requires it, a participant will not be told of his or her *APOE* ε4 status. Individual participant *APOE* ε4 genotype results will be blinded to participants, investigators, and the Sponsor. *APOE* ε4 status information will be supplied directly to the IxRS vendor by the central testing laboratory so that the information can be incorporated at the time of randomization. For participants for whom *APOE* ε4 status is already known, the results will be blinded to the Sponsor and as much as possible to the site and central MRI reader.

The study is to be conducted in a double-blind manner to minimize potential bias from investigators and participants. The Sponsor will be blinded to study treatment. Sponsor, participants, and site staff will remain blinded to previous treatment allocation in the OLE period. The Master Randomization or Master Medication List will not be available at the study center, to Roche monitors, Roche project statisticians, or to the project team at Roche. Unblinding should not occur except in the case of emergency situations where knowledge of the study drug assigned would affect participant care. The investigator should make every effort to contact Roche before unblinding a participant. In the event that the investigator unblinds a participant without prior notification, the investigator must contact Roche within 1 working day of the event. Any request from the investigator for information about the treatment administered to study participants for another purpose must be discussed with the Medical Monitor.

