4.3.2.1 Gantenerumab and Placebo Administration during Double-Blind Treatment Period

Gantenerumab or placebo will be administered by SC injection to all participants.

Gantenerumab will be administered by SC injection to all participants randomized to the active treatment arm, regardless of *APOE* ϵ 4 status, at a dose of 120 mg SC Q4W for 3 months, 255 mg SC Q4W for 3 months, and 510 mg SC Q4W for 3 months, prior to reaching the target dose (see [Figure 8](#)). Once the target dose is reached, study drug will be administered every 2 weeks (Q2W administration of 510 mg SC gantenerumab). The switch to a Q2W administration schedule allows decreasing the number of SC administrations in the abdomen per visit.

Note: A minimum of 3 doses during each dosing step must be administered prior to up-titration.

Figure 8 Overall Gantenerumab Dosing Design in the Double-Blind Treatment Period

Q2W = every 2 weeks; Q4W = every 4 weeks; SC = subcutaneous.

For Q4W injections, a time window of ± 7 days is allowed for dosing visits. For Q4W injections, the recommended minimum time between doses is 3 weeks. The maximum recommended time between doses should not exceed 6 weeks. Once study drug is administered Q2W, the time window for dosing visits is ± 3 days. For Q2W injections, the recommendation is not to administer more than 1020 mg (i.e., 2 times 510 mg Q2W) within 28 days. Always return to the initial planned schedule per randomization for subsequent visits.

Regardless of dose, each participant will undergo up to a total of 49 dosing visits in scenario 1 or 55 dosing visits in scenario 2 (if applicable, see Section 3.3.1) in the double-blind treatment period of the study. Participants who have completed the double-blind treatment period at the time of the implementation of *the 12 week study extension*, will have undergone up to 43 dosing visits. Injections will be administered as one 0.8-mL (120-mg dose), one 1.7-mL (255-mg dose), or two 1.7-mL injections (510-mg dose) subcutaneously to the abdomen, respectively.

Placebo of identical composition (except protein) and identical volume to gantenerumab will be administered by SC injection to all participants randomized to placebo at the same frequency and using the same route of administration.

On study drug administration days that include efficacy assessments (see the schedule of activities in Appendix 1), study drug must be administered at the clinical site. Study

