MRI scans will be reviewed by a central MRI core laboratory, which will perform the diagnostic reads and assessment of MRI outcome measures. MRI scans should preferably be transferred to the central MRI core laboratory electronically. Data transfer from individual study sites to the central MRI core laboratory may take up to 7–10 days, if not done electronically. Upon receipt of the MRI scans from the study sites, the central MRI core laboratory will provide the diagnostic reads. MRI results must be made available to investigators prior to next dosing (refer to Section 5.1.2 for additional details on MRI safety management).

MRI facility qualification and scan quality control will be performed by the central MRI core laboratory.

Additional instructions regarding the procedures for MRI scan acquisition and transmittal to the central reading facility can be found in the MRI Manual.

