5.1.1 Risks Associated with Gantenerumab

5.1.1.1 Amyloid-Related Imaging Abnormalities

To date, clinical experience with gantenerumab reveals that ARIA events are dose-dependent and *APOE* ϵ 4 dependent. These events are manageable with MRI monitoring and dose intervention algorithms. In addition, in case of clinical symptoms, the use of IV glucocorticosteroids may be considered.

Rules for management of participants who develop ARIA-E or ARIA-H are provided in [Appendix 6](#).

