5.1.2 Management of Participants Who Experience Selected Adverse Events

Participants will undergo brain MRI examinations prior to every dose increase (pre-uptitration MRI scans) and according to the schedule of activities once the target dose is achieved. The pre-uptitration MRI scans will determine eligibility for the next uptitration dose. In the double-blind treatment period, a minimum of 3 doses of each dosing step have to be administered before the participant is eligible for the next uptitration dose. In the OLE, a minimum of 3 doses of each dosing step must be administered prior to be eligible for uptitration. In the OLE, a dose is defined as two consecutive dosing visits (one with an even dose number and one with an odd dose number, see [Table 4](#), Section [4.3.2.2](#)).

Participants will be eligible for uptitration if there are no new ARIA-E, if the ARIA-E is resolved (BGTS=0), and if the criteria for discontinuation because of ARIA-H have not been met.

In addition, the following dose adjustment and discontinuation rules for MRI findings will apply:

- In case of asymptomatic ARIA-E ≥ 1 and < 4 BGTS: Continue study drug at the same dose level (i.e., do not uptitrate) and repeat MRI 4 weeks later.

As long as BGTS is < 4 and ≥ 1 , continue study drug at the same dose level and continue MRI monitoring at 4-week intervals until the event resolves. When ARIA-E resolves, resume uptitration and MRI monitoring according to the schedule of activities.

If BGTS ≥ 4 or symptoms develop, refer to the rule below.

- In case of occurrence of symptoms in the presence of ARIA-E (any size) or asymptomatic ARIA-E with ≥ 4 BGTS: Temporarily interrupt study drug (but continue all assessments per schedule of activities) and implement MRI monitoring performed at 4-week intervals until symptoms and ARIA resolve.

When symptoms and ARIA-E resolve, reintroduce study drug at the next scheduled dosing visit, at the same dose given at the time the event was detected and perform an MRI scan after the first dose for participants on Q4W regimen and after the second dose for participants on the Q2W regimen.

If no new ARIA-E is detected, resume uptitration and obtain an MRI scan per the titration schedule. For participants on the Q2W regimen, perform another MRI scan 3 months after study drug reintroduction.

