Appendix 6 Management Rules for Amyloid-Related Imaging Abnormalities

Event	Characteristics	Action to Be Taken
ARIA-E	Asymptomatic ARIA-E and BGTS <4	
 • Continue study drug at the same dose level (i.e., do not uptitrate) and repeat MRI scan 4 weeks later. 
 – As long as BGTS is <4 and ≥ 1, continue study drug at the same dose level and repeat MRI 4 weeks later. – Once ARIA resolves, resume uptitration and obtain an MRI scan per the titration schedule. For participants randomized to the Q2W regimen, perform another MRI scan 3 months after ARIA resolution.
	Symptomatic ARIA-E (of any size) or asymptomatic ARIA-E and BGTS ≥ 4	
 • Temporarily interrupt study drug and perform MRI scans at 4-week intervals until symptoms and ARIA-E resolve. • When symptoms and ARIA-E resolve, reintroduce study drug at dose given at the time the event was detected. 
 – Perform an MRI scan before next scheduled dose for participants randomized to the Q4W regimen or after the second dose for participant randomized to the Q2W regimen. – If no new ARIA-E is detected, resume uptitration and obtain an MRI per titration schedule. For participants randomized to the Q2W regimen, perform another MRI scan 3 months after study drug reintroduction.
	Any recurrence of ARIA-E	
 • Treat the same as the first event (based on symptoms and BGTS).
ARIA-H	>15 ARIA-H cumulatively (should not include any disseminated LH)	
 • Discontinue study drug.

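### After mild asymptomatic ARIA-E on 510 mg Q2W, Section 5.1.2 leaves out the 3-month follow-up MRI that Appendix 6 requires

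*Protocol*

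**What the plan says.** The ARIA-E rules appear twice in the protocol.

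- **Section 5.1.2, asymptomatic, BGTS 1 to below 4.** Dosing continues at the same level with MRI every 4 weeks. Then: "When ARIA-E resolves, resume uptitration and MRI monitoring according to the schedule of activities". Nothing further is required.
- **Appendix 6, same event.** "Once ARIA resolves, resume uptitration and obtain an MRI scan per the titration schedule. For participants randomized to the Q2W regimen, perform another MRI scan", and the table times that extra scan at 3 months after the ARIA has resolved.
- **Section 5.1.2, symptomatic or BGTS of 4 or more.** The rule is "Temporarily interrupt study drug (but continue all assessments per schedule of activities"), with 4-weekly MRI until resolution. After dosing restarts: "For participants on the Q2W regimen, perform another MRI scan 3 months after study drug reintroduction".

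The cross-references split. Section 5.1.1.1 points to Appendix 6: "Rules for management of participants who develop ARIA-E or ARIA-H are provided in" that appendix. Section 4.5.9 points to the body text ("refer to Section 5.1.2 for additional details on MRI safety management"), and so does Section 4.6.5 for new MRI findings. Section 5.1.2 does not cite Appendix 6.

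On regimen, Section 4.2 says "participants who meet all eligibility criteria will be randomly assigned to one of two treatment groups (gantenerumab or placebo"), and Section 4.3.2.1 says "Once the target dose is reached, study drug will be administered every 2 weeks (Q2W administration of 510 mg SC gantenerumab").

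**The concern.** Two operative texts give different follow-up for the same finding, and the one without the extra scan is the one sites are mostly directed to. The 3-month scan on the other path of Section 5.1.2 cannot fill the gap. It runs from drug reintroduction, and below BGTS 4 without symptoms the drug is never stopped.

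The stake is specific. A recurrence with BGTS of 4 or more requires interruption even without symptoms, and a silent one is found only by MRI. If the 3-month scan is skipped, 510 mg Q2W could continue through it until the next scheduled scan. The concern goes no wider than this. A silent recurrence below BGTS 4 would not stop dosing under either text. A symptomatic one has other routes to detection, because adverse events are recorded at dosing visits and unscheduled MRI is allowed.

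The Appendix 6 wording is a second, smaller fault. It addresses participants randomized to a Q2W or Q4W regimen, but randomization is only to gantenerumab or placebo, and everyone who reaches target dose moves to Q2W. Taken literally the instruction covers no one, although the intended meaning can be inferred.

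**Working it through.** The plan states no figure for this delay, so there is none to reproduce. The check is date arithmetic on nominal visit weeks.

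**Inputs**

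- Scheduled MRI (Appendix 1, Tables 2 and 3): Weeks 36, 48, 60, 76, 104 and 116. The Week 36 scan precedes the first Q2W dose. Successive gaps are 12, 12, 16, 28 and 12 weeks.
- Rescan interval while ARIA-E persists (Section 5.1.2): 4 weeks.
- 3 months: 12 weeks on the protocol's own usage (Appendix 1 Table 3 labels Week 104 to 116 a 3-month extension), or 13 weeks by the calendar.

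**Formulas**, with R the week of resolution:

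- Gap = next scheduled MRI − R
- Delay = max(0, gap − 13) to max(0, gap − 12)

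| Resolution week R | Next scheduled MRI | Gap (weeks) | Delay past the 3-month point (weeks) |
|---|---|---|---|
| 60 | 76 | 16 | 3–4 |
| 63 | 76 | 13 | 0–1 |
| 64 | 76 | 12 | 0 |
| 76 | 104 | 28 | 15–16 |
| 80 | 104 | 24 | 11–12 |
| 84 | 104 | 20 | 7–8 |
| 88 | 104 | 16 | 3–4 |
| 91 | 104 | 13 | 0–1 |
| 92 | 104 | 12 | 0 |
| 104 | 116 | 12 | 0 |

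**Reading the table**

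- An event first seen at Week 76 and rescanned every 4 weeks can resolve at Week 80 at the earliest. The Appendix 6 scan is then due at 80 + 12 = 92 or 80 + 13 = 93, and the delay is 104 − 92 = 12 or 104 − 93 = 11 weeks.
- The 15–16 week extreme needs an event found on an earlier scan that resolves on the Week 76 scan itself.
- A scheduled scan at or before the 3-month point counts as no delay. That is lenient. Resolution at Week 72 scores zero because of the Week 76 scan, although the Appendix 6 scan due at 72 + 12 = 84 or 72 + 13 = 85 would still not be done.
- MRI must be done at least 7 days before dosing. If that moves only the Week 104 scan, to Week 103, the Week 80 delay becomes 10–11 weeks. If the Week 76 scan and its rescan also move a week earlier, the delay is unchanged.

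**The case against.** The best reply is that this is an omission rather than a contradiction. Section 5.1.2 does not forbid the scan, a site that performs it complies with both texts, and Section 5.1.1.1, shortly before, names Appendix 6 as the source of the ARIA rules. In Appendix 6 the words fixing the timing to ARIA resolution are italicised, the protocol's mark for new material in Version 5, so the sponsor's current intent is clear. Nothing in the documents shows that sites would ignore the appendix.

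The risk is also small. In Study WN25203 (Section 1.2.3), new ARIA-E was most frequent at 3 to 6 months and fell substantially after the first year, although at lower doses. The schedule already accepts 28 weeks between scans (Week 76 to 104) for everyone. Investigators may add MRI at any time, and the iDMC reviews ARIA unblinded.

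Most of this stands as a limit on size, and Week 80 is close to the worst case. It does not remove the fault. The italics suggest that an update was made in the appendix and not carried into Section 5.1.2. Optional MRI is not a required scan, and the 28-week interval was not set for participants who have just had ARIA-E. Nor is silent, high-scoring ARIA-E unusual at high dose. In the two earlier open-label extensions (Section 1.2.3), 11 of 47 and 18 of 71 patients with new ARIA-E reported CNS events, together 29 of 118, and median maximum BGTS was 7.0 and 9.0. Those were new events under other titration schedules, so they are not recurrence rates.

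**Conclusion.** The concern holds. For asymptomatic ARIA-E with BGTS 1 to below 4 on Q2W dosing, Section 5.1.2 omits a scan that Appendix 6 requires. A site following Section 5.1.2 as written would skip it.

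For an event found at Week 76, the resulting delay is at most 11–12 weeks. It is nil for resolution from Week 92 onward, and up to 3–4 weeks for resolution at Weeks 60–63. These figures assume nominal visit weeks, 3 months equal to 12–13 weeks, 4-weekly rescanning, and no discretionary MRI. The documents give no rate for this path, so the number affected cannot be estimated; it is likely to be small. The efficacy analysis is not affected. This should be corrected because it is an error in an operative safety rule and costs almost nothing to repair.

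**What to change.** 1. In Section 5.1.2, add to the bullet for BGTS below 4: *For participants on the Q2W regimen, perform another MRI scan 3 months after ARIA resolution.*
2. In Appendix 6, replace *randomized to* with *on* in the three references to the Q2W regimen and the one to the Q4W regimen. Section 5.1.2 already words it this way.
3. Optionally, add a footnote to the MRI row of Appendix 1 Table 2. Table 3 needs none, since the computed delay from Week 104 to 116 is zero.

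The cost is one sentence and four small wording changes, by clarification letter or in the next amendment. No scans are added beyond those Appendix 6 already requires.

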5.2 SAFETY PARAMETERS AND DEFINITIONS

Safety assessments will consist of monitoring and recording adverse events, including serious adverse events and adverse events of special interest, performing protocol-specified safety laboratory assessments, measuring protocol-specified vital signs, and conducting other protocol-specified tests that are deemed critical to the safety evaluation of the study.

Certain types of events require immediate reporting to the Sponsor, as outlined in Section 5.4.

5.2.1 Adverse Events

According to the ICH guideline for Good Clinical Practice, an adverse event is any untoward medical occurrence in a clinical investigation subject administered a

pharmaceutical product, regardless of causal attribution. An adverse event can therefore be any of the following:

- Any unfavorable and unintended sign (including an abnormal laboratory finding), symptom, or disease temporally associated with the use of a medicinal product, whether or not considered related to the medicinal product
- Any new disease or exacerbation of an existing disease (a worsening in the character, frequency, or severity of a known condition), except as described in Section 5.3.5.10
- Recurrence of an intermittent medical condition (e.g., headache) not present at baseline
- Any deterioration in a laboratory value or other clinical test (e.g., ECG, X-ray) that is associated with symptoms or leads to a change in study treatment or concomitant treatment or discontinuation from study drug
- Adverse events that are related to a protocol-mandated intervention, including those that occur prior to assignment of study treatment (e.g., screening invasive procedures such as biopsies)

5.2.2 Serious Adverse Events (Immediately Reportable to the Sponsor)

A serious adverse event is any adverse event that meets any of the following criteria:

- Is fatal (i.e., the adverse event actually causes or leads to death)
- Is life threatening (i.e., the adverse event, in the view of the investigator, places the participant at immediate risk of death)
 - This does not include any adverse event that had it occurred in a more severe form or was allowed to continue might have caused death.
- Requires or prolongs inpatient hospitalization (see Section 5.3.5.12)
- Results in persistent or significant disability/incapacity (i.e., the adverse event results in substantial disruption of the participant's ability to conduct normal life functions)
- Is a congenital anomaly/birth defect in a neonate/infant born to a mother exposed to study drug
- Is a significant medical event in the investigator's judgment (e.g., may jeopardize the participant or may require medical/surgical intervention to prevent one of the outcomes listed above)

The terms "severe" and "serious" are not synonymous. Severity refers to the intensity of an adverse event (e.g., rated as mild, moderate, or severe; the event itself may be of relatively minor medical significance (such as severe headache without any further findings).

Severity and seriousness need to be independently assessed for each adverse event recorded on the eCRF.

Serious adverse events are required to be reported by the investigator to the Sponsor immediately (i.e., no more than 24 hours after learning of the event; see Section 5.4.2 for reporting instructions).

5.2.3 Adverse Events of Special Interest (Immediately Reportable to the Sponsor)

Adverse events of special interest are required to be reported by the investigator to the Sponsor immediately (i.e., no more than 24 hours after learning of the event; see Section 5.4.2 for reporting instructions). Adverse events of special interest for this study include the following:

- Cases of potential drug-induced liver injury that include an elevated ALT or AST in combination with either an elevated bilirubin or clinical jaundice, as defined by Hy's Law (see Section 5.3.5.8)
- Suspected transmission of an infectious agent by the study drug, as defined below
Any organism, virus, or infectious particle (e.g., prion protein transmitting transmissible spongiform encephalopathy), pathogenic or non-pathogenic, is considered an infectious agent. A transmission of an infectious agent may be suspected from clinical symptoms or laboratory findings that indicate an infection in a participant exposed to a medicinal product. This term applies only when a contamination of the study drug is suspected.

5.2.4 Selected Adverse Events

Data on associated symptoms and safety MRI scans will be collected for the following selected adverse events:

- ARIA-E: ARIAs suggestive of vasogenic edema and sulcal effusions
- ARIA-H: ARIAs suggestive of microhemorrhages and/or hemosiderin deposits

Please refer also to Section 5.3.5.1 for further details how to report ARIA events.

5.3 METHODS AND TIMING FOR CAPTURING AND ASSESSING SAFETY PARAMETERS

The investigator is responsible for ensuring that all adverse events (see Section 5.2.1 for definition) are recorded on the Adverse Event eCRF and reported to the Sponsor in accordance with instructions provided in this section and in Sections 5.4–5.6.

For each adverse event recorded on the Adverse Event eCRF, the investigator will make an assessment of seriousness (see Section 5.2.2 for seriousness criteria), severity (see Section 5.3.3), and causality (see Section 5.3.4). The investigator is also responsible for reporting medical device complaints (see Section 5.4.4).

5.3.1 Adverse Event Reporting Period

Investigators will seek information on adverse events at each participant contact. All adverse events, whether reported by the participant, the study partner, or noted by study

personnel, will be recorded in the participant's medical record and on the Adverse Event eCRF.

After informed consent has been obtained but prior to initiation of study drug, only serious adverse events caused by a protocol-mandated intervention (e.g., invasive procedures such as biopsies, discontinuation of medications) should be reported (see Section 5.4.2 for instructions for reporting serious adverse events).

In addition, after administration of a PET ligand, but prior to initiation of study drug, the following adverse events should be reported:

- All adverse events (serious or non-serious) believed to be related to a PET ligand
- All serious adverse events occurring within 48 hours of PET ligand administration regardless of relatedness to the PET ligand

For reporting of serious adverse events, see Section 5.4.2 for instructions. For non-serious PET ligand adverse events, a PET ligand specific non-serious adverse event reporting paper form should be completed and submitted to the Sponsor or its designee by scanning and emailing the form using the email address provided on the form.

After initiation of study drug, all adverse events will be reported until the participant's last visit (including long-term follow-up visits).

Instructions for reporting adverse events that occur after the adverse event reporting period are provided in Section 5.6.

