**Table 2 Analysis Sets (cont.)**

Analysis set	Definition	Scope
Amyloid PET modified intent-to-treat (Amyloid-PET-mITT)	All participants in the ITT analysis set who participated in the Amyloid PET sub-study and who had at least one Amyloid PET scan with a valid quantitative measurement performed with either florbetaben or flutemetamol and who did not withdraw from the Amyloid PET substudy before randomization.	All analyses of Amyloid PET parameters will be based on this analysis set
Amyloid-PET-longitudinal	Analysis using this analysis set will be performed by randomized treatment. All participants in the Amyloid-PET-mITT with a valid post-baseline quantitative amyloid PET measurement performed with either florbetaben or flutemetamol.	Summary of treatment group comparability will also be repeated on this analysis set.
Safety-evaluable	All participants randomized during the global enrollment phase who received at least one dose of study drug. Any participant randomized to placebo who received at least one dose (any dose) of active drug will be summarized as having received the active drug. Analysis using this analysis set will be performed by treatment actually received.	All safety analyses (with the exception of Safety MRI) will be based on this analysis set.
MRI Safety-evaluable	All participants in the Safety-evaluable analysis set who had at least one post-baseline safety MRI scan. Analysis using this analysis set will be performed by treatment actually received	All analyses of safety MRI will be based on this analysis set.
Amyloid-PET Safety Evaluable	All participants in the Safety-evaluable analysis set who received at least one dose of radioligand Analysis using this analysis set will be performed by treatment actually received	All safety analysis for the amyloid-PET sub-study will be based on this analysis set.
Tau-PET Safety Evaluable	All participants in the Safety-evaluable analysis set who received at least one dose of radioligand. Analysis using this analysis set will be performed by treatment actually received	All safety analysis for the tau-PET sub-study will be based on this analysis set.

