## **5.6 SAFETY ANALYSES**

Descriptive statistics will be used to analyze all safety data collected in the double-blind treatment period in the safety-evaluable analysis set, unless otherwise specified.

Safety data collected from the day of the first dose of blinded study drug up to 14 weeks after the last dose of blinded study drug (but no later than the day before the first OLE dose for the participants who entered the OLE period) will be included in the

beyond the 14-week post last dose period and until the end of the study will be included in the follow-up period analyses.

For participants who entered the OLE period, safety data collected from the day of the first OLE dose up to 14 weeks after the last OLE dose will be included in the OLE period analyses

Safety analyses will be assessed through summaries of exposure to study treatment, adverse events, changes in laboratory test results (including shift tables), MRI findings, changes in vital signs and ECGs, and changes in C-SSRS scores.

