### **5.6.2            Adverse Events**

All verbatim AEs terms will be coded using the Medical Dictionary for Regulatory Activities (MedDRA) version that is current at the time of the analysis (Version 25.0 or higher), and AE severity will be graded according to the scale defined in Table 5 in Section 5.3.3 of the study protocol (mild/moderate/severe). For each treatment group, the frequency of each AE preferred term will be defined as the number of participants experiencing at least one occurrence of the event. Each table will present the overall number and percentage of participants experiencing at least one AE and the total number of AEs reported. Percentages will be based on the number of participants in the safety-evaluable analysis set. In summary tables, AEs will be sorted by body system (in decreasing order of overall incidence), then by preferred term (in decreasing order of overall incidence). The summary tables will be restricted to treatment-emergent AEs, i.e., AEs that occur on or after the day of first dose of study drug. Non-treatment-emergent AEs (with onset before the first dose) will be listed.

The following safety information will be summarized by treatment group for the double-blind treatment period:

- AEs, AEs by intensity, AEs related to study drug
- Deaths
- SAEs, SAEs related to study drug
- AEs leading to discontinuation of study treatment

- AEs leading to dose modifications (dose interruption, dose reduction or delayed up-titration). Delayed up-titration at any given visit is defined as the simultaneous occurrence of the following two tick-boxes in the eCRF Adverse Events form:
  - Action take with Gantenerumab due to AE/SAE: Dose Not Changed
  - Was dose regimen modified from protocol schedule? Yes"
- Injection site reaction (ISR) signs and symptoms
- Systemic injection reactions (AEs with eCRF tickbox “systemic injection reaction” selected)
- ‘Hypersensitivity reactions’

Protocol-specified adverse events of special interest (AESI) will be listed.

The impact of the COVID-19 pandemic on the safety data will be assessed by reviewing the following:

- Confirmed or suspected COVID-19 AEs
- AEs associated with COVID-19
- Potential long COVID-19 symptoms

The following data handling rules will be applied for all AE summary tables:

- Events that are missing both at onset and at end dates will be considered to have started after the first dose of study drug and the duration will be set to missing.

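### The SAP runs PET-substudy safety on the study-drug clock: as written, adverse events after a pre-dose PET scan would be listed but not summarised, and substudy participants given ligand but never dosed are left out

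*Protocol*

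**What the plan says.** **Collection.** Protocol 5.3.1 sets a reporting rule for the time between a PET ligand dose and the start of study drug: "after administration of a PET ligand, but prior to initiation of study drug, the following adverse events should be reported". It names two kinds of event: "All adverse events (serious or non-serious) believed to be related to a PET ligand", and "All serious adverse events occurring within 48 hours of PET ligand administration regardless of relatedness to the PET ligand". Protocol 5.4.2.1 repeats the serious-event part. For non-serious ligand events, "a PET ligand specific non-serious adverse event reporting paper form should be completed" and sent to the sponsor.

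**Analysis sets.** SAP Table 2 defines the Amyloid-PET and Tau-PET Safety Evaluable sets in the same words: "All participants in the Safety-evaluable analysis set who received at least one dose of radioligand". The parent set is "All participants randomized during the global enrollment phase who received at least one dose of study drug". Table 2 assigns all safety analysis of each substudy to its PET set. It names no ligand and puts no limit on when the ligand was given.

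**Analysis period and tables.** SAP 5.6 takes as its double-blind safety period "Safety data collected from the day of the first dose of blinded study drug up to 14 weeks after the last dose" (with an earlier cut-off for those entering the open-label extension). SAP 5.6.2 then says: "The summary tables will be restricted to treatment-emergent AEs, i.e., AEs that occur on or after the day of first dose of study drug". Events with earlier onset are listed. SAP 5.7.5 and 5.7.6, which cover the two substudies, contain no adverse event rules.

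**The concern.** The protocol treats the tracer as an exposure in its own right and collects reactions to it before gantenerumab or placebo is given. The SAP creates populations for PET-substudy safety but supplies only a study-drug clock for them. For a tracer question, the relevant start is the ligand injection. With the study-drug start instead, the first tracer exposure, when a reaction in a tracer-naive person would first be seen, is normally the one whose events cannot be tabulated.

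At stake is the summary of tracer tolerability. This matters most for [18F]GTP1, which Protocol 3.1.2 describes as investigational. The information is gathered, but the SAP has no rule that turns it into an incidence.

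**Working it through.** The plan states no figure on this point, so there is nothing to reproduce. The check sets the rules side by side and then illustrates the size.

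**1. Who is in the set, and where is the event shown?** Applying SAP Table 2, 5.6 and 5.6.2 literally:

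| Participant | In PET safety set? | Pre-dose tracer event |
|---|---|---|
| Scanned before dosing, then dosed, later scans | Yes | Listing only; events after later scans are tabulated |
| Scanned before dosing, then dosed, no later scan | Yes | Listing only |
| Scanned in the substudy, never dosed | No | Outside the set and the tables |

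**2. Is the baseline scan before dosing?** Normally yes. Protocol 4.6.1 allows scans for substudy volunteers once the other screening results are in, and asks for time to complete and evaluate them before screening ends. The PET modified-ITT definitions in SAP Table 2 exclude people who left the substudy before randomization. SAP Tables 7 and 9 accept a baseline scan up to Day 35, but that is an analysis window, not a schedule.

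**3. How many exposures are affected?** SAP Tables 7 and 9 give three scan times: baseline, Week 52 and Week 116. With full follow-up, 1 of 3 falls outside the table window. With only one later scan it is 1 of 2, and with none it is 1 of 1.

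**4. Illustration of size.** Assume a risk p of a tracer event per scan, the same at every scan and independent between scans, with one pre-dose scan and k later scans. None of these risks is in the documents.

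- Participants with an event, all scans: 1 − (1 − p)^(k+1)
- Participants with an event that the tables count: 1 − (1 − p)^k
- Share missed: 1 minus the ratio of the second to the first

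| p | k | All scans | Tabulated | Share missed |
|---|---|---|---|---|
| 0.5% | 2 | 1.49% | 1.00% | 33.2% |
| 1% | 2 | 2.97% | 1.99% | 33.0% |
| 5% | 2 | 14.26% | 9.75% | 31.6% |
| 1% | 1 | 1.99% | 1.00% | 49.7% |
| 1% | 0 | 1.00% | 0.00% | 100% |

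Worked line for p = 1%, k = 2: 1 − 0.99³ = 0.0297; 1 − 0.99² = 0.0199; 1 − 0.0199/0.0297 = 0.33.

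If the first exposure carried r times the later risk (again an assumption), the counted share of events would be about 2/(2 + r): 0.67, 0.50 and 0.29 for r = 1, 2 and 5.

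**The case against.** The strongest reply is that the SAP plans no tracer incidence at all. It defines two PET sets but describes no PET adverse event table, and 5.6.2 bases percentages on the overall safety-evaluable set. The PET sets are analysed by treatment actually received, which is a study-drug grouping. For a gantenerumab-versus-placebo table, leaving out events before the first dose is conventional. The substudies also have their own protocols, not available here, which may hold tracer-specific rules. And tracer safety has another route: Protocol 5.4.2.1 requires pre-dose serious events to be reported within 24 hours, and Protocol 5.7 compares cumulative frequency with each tracer's Investigator's Brochure.

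Much of this stands as a limit on the point. The mismatch arises from applying the general rules to the PET sets, not from a specified table. It does not remove the point. Table 2 does assign the substudies' safety analysis to those sets, and the SAP offers no other rule for them. Expedited reporting serves individual cases and expectedness; it does not replace a tabulation in the study report.

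A reader might go further and infer three things that the documents do not support:

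- *That a participant who reacted only to the first scan is reported as event-free.* SAP 5.6.2 lists events with onset before the first dose.
- *That baseline exposures always sit in a denominator and never in a numerator.* The sets count participants, not exposures. An event with both dates missing is assigned to the period after dosing, and a baseline scan performed after dosing would have its events tabulated.
- *That non-serious ligand events bypass the eCRF.* Protocol 5.3 and 5.3.1 also say in general that adverse events go on the Adverse Event eCRF. Whether the paper form replaces or supplements it is unclear.

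**Conclusion.** The gap is real and worth correcting. It rests on two conditions: that the general rules of SAP 5.6 and 5.6.2 govern the PET safety sets, as the SAP implies by giving no others, and that the substudy protocols do not say otherwise. Under those conditions the loss is from summary tables, not from reporting altogether, and it concerns normally one of three scheduled scan times plus any substudy participants scanned but never dosed.

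The documents do not fix the size in percentage terms. The one-third figure holds only for three scans of equal risk, and the larger losses need fewer scans or a higher first-exposure risk. The study-drug safety comparison and all efficacy conclusions are untouched.

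**What to change.** **SAP Table 2.** Define each PET safety set as participants enrolled in that substudy who received a dose of its ligand, whether or not they went on to study drug. Name the ligands. Show never-dosed participants in a separate column, since they have no treatment received. Do not include screen failures outside the substudy.

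**SAP 5.6.2.** Add one table per tracer with two parts:

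- events collected before study drug under Protocol 5.3.1 (ligand-related events, and serious events within 48 hours);
- adverse and serious adverse events with onset within 48 hours of each later ligand dose, identified by date.

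The date rule is needed because Protocol 5.3.4 records relatedness to study drug only, so no new causality field is required. The two parts use different rules and should be shown separately.

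**Data flow.** State that ligand events reported on paper are entered in the clinical database and included in both the tables and the listing.

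Leave the study-drug adverse event tables as they are. The cost is some programming and data entry, and a slightly less favourable tracer event rate.
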